# Proprietary Information of MD Anderson

Protocol # 2016-0251

Date: February 24, 2020

100

6% (35/561) at position M28, 2% (11/561) at position Q30, 3% (15/561) at position L31, and 2% (10/561) at position Y93. Polymorphisms at NS5A position H58 were common (10%) and were not associated with reduced Zepatier efficacy, except for a single virologic failure subject whose virus had baseline M28V and H58D polymorphisms.

The SVR12 rates for subjects treated with Zepatier for 12 weeks were 88% (29/33) for subjects with M28V/T/L polymorphisms (n=29, 3, and 1, respectively), 40% (4/10) for subjects with Q30H/R/L polymorphisms (n=5, 3, and 2, respectively), 38% (5/13) for subjects with an L31M polymorphism, and 63% (5/8) for subjects with Y93C/H/N/S polymorphisms (n=3, 3, 1, and 1, respectively). Although data are limited, among GT1a-infected subjects with these NS5A polymorphisms who received Zepatier plus RBV for 16 weeks, 6 out of 6 subjects achieved SVR12. The specific NS5A polymorphisms observed in subjects treated with Zepatier plus RBV for 16 weeks included M28V (n=2), Q30H (n=1), L31M (n=2), or Y93C/H (n=1 each).

Table 14 SVR12 in HCV Genotype 1a-Infected Subjects without or with Baseline NS5A Polymorphisms

NS5A Polymorphism Status	Zepatier 12 Weeks SVR12 % (n/N)	Zepatier + RBV 16 Weeks SVR12 % (n/N)
Without baseline NS5A polymorphism (M28, Q30, L31, or Y93)	98% (441/450)	100% (49/49)
With baseline NS5A polymorphism (M28*, Q30*, L31*, or Y93*)	70% (39/56)	100% (6/6)

\*Any change from GT1a reference.

There are insufficient data to determine the impact of HCV NS5A amino acid polymorphisms in treatment-experienced subjects who failed prior Peg-IFN + RBV + HCV protease inhibitor therapy and received Zepatier with RBV.

In GT1a-infected subjects, the NS3 Q80K polymorphism did not impact treatment response. Polymorphisms at other NS3 RAVs were uncommon and were not associated with reduced treatment efficacy.

## *Genotype 1b*

In GT1b-infected subjects treated with Zepatier for 12 weeks, SVR12 rates (non-virologic failure-censored) were 94% (48/51) and 99% (247/248) for those with and without one or more NS5A polymorphisms at position 28, 30, 31, or 93. In GT1b-infected subjects, baseline NS3 polymorphisms did not impact treatment response.

# Proprietary Information of MD Anderson

Protocol # 2016-0251

Date: February 24, 2020

101

## Effect of Baseline HCV Polymorphisms on Treatment Response in Genotype 4-Infected Subjects

Phylogenetic analysis of HCV sequences from GT4-infected subjects (n=71) in the pooled analyses of subjects (non-virologic failure-censored) treated with regimens containing Zepatier with or without RBV in Phase 2 and 3 clinical trials identified 4 HCV GT4 subtypes (4a, 4d, 4k, 4o). Most subjects were infected with either subtype 4a (42%) or 4d (51%); 1 to 2 subjects were infected with each of the other GT4 subtypes. Among subjects enrolled at US study sites, 11/13 (85%) were infected with HCV subtype 4a. There were 2 subjects infected with HCV subtype 4d who experienced virologic failure with the regimen containing grazoprevir and elbasvir.

In GT4-infected subjects, SVR12 rates for subjects with baseline NS5A polymorphisms (any change from reference at NS5A amino acid positions 28, 30, 31, 58, and 93 by population nucleotide sequencing) were 100% (28/28) and for subjects without baseline NS5A polymorphisms were 95% (41/43).

In GT4-infected subjects, SVR12 rates for subjects with baseline NS3 polymorphisms (any change from reference at NS3 amino acid positions 36, 54, 55, 56, 80, 107, 122, 132, 155, 156, 158, 168, 170, and 175 by population nucleotide sequencing) were 100% (18/18) and for subjects without baseline NS3 polymorphisms were 96% (51/53).

## Cross Resistance

Cross resistance is possible among NS5A inhibitors and NS3/4A protease inhibitors by class. Elbasvir and grazoprevir are fully active against viral populations with substitutions conferring resistance to NS5B inhibitors.

In the C-SALVAGE trial, subjects with GT1 infection who had failed prior treatment with boceprevir (n=28), simeprevir (n=8), or telaprevir (n=43) in combination with PegIFN plus RBV received elbasvir 50 mg qday + grazoprevir 100 mg qday + RBV for 12 weeks. There are limited data to determine the impact of HCV NS3 RAVs detected at baseline in treatment-experienced subjects who failed prior Peg-IFN + RBV + HCV protease inhibitor therapy and received Zepatier with RBV. SVR was achieved in 88% (21/24) of GT1a and GT1b infected subjects with NS3 RAVs detected at baseline. Specific NS3 substitutions observed at baseline included one or more of the following: V36L/M (n=8), T54S (n=4), S122G/T (n=9), R155K/T (n=9), A156S/T (n=1), and D168E/N (n=3). SVR was 100% (55/55) in subjects without baseline NS3 resistance substitutions. The 3 virologic failure subjects had the following NS3 or NS5A substitutions/polymorphisms at baseline: NS3 R155T/D168N, NS3 R155K plus NS5A H58D, and NS3 T54S plus NS5A L31M.

The efficacy of Zepatier has not been established in patients who have previously failed treatment with other regimens that included an NS5A inhibitor.

# Proprietary Information of MD Anderson

Protocol # 2016-0251

Date: February 24, 2020

102

## 7.1.4.2.3 HCV Genomic Exploratory Measurements

Understanding genetic determinants of drug response is an important endeavor during medical research. This research will evaluate whether genetic variation within a clinical trial population correlates with response to the treatment(s) under evaluation. If genetic variation is found to predict efficacy or adverse events, the data might inform optimal use of therapies in the patient population. A biosample will be collected and may be used for exploring the relationship between genetic variation and subject response to the treatment(s) administered. Variation across the human genome may be analyzed for association with clinical data collected in this study (For example: to assess the genetic variation in the humanrs12979860 genotype (previously known as Interleukin 28B genotype) as a predictor of virologic response in each treatment arm, for ADME and HLA genes associated with liver injury). This research contributes to understanding genetic determinants of efficacy and toxicity associated with the treatments in this study. Pharmacogenomic data from this study may be combined with data from other studies using these treatments.

## 7.1.5 Other Procedures

### 7.1.5.1 Withdrawal/Discontinuation

Subjects who discontinue/withdraw from treatment prior to completion of the treatment regimen should be encouraged to continue to be followed for all remaining study visits.

When a subject discontinues/withdraws prior to trial completion, all applicable activities scheduled for the end of study visit should be performed at the time of discontinuation. Any AEs which are present at the time of discontinuation/withdrawal should be followed in accordance with the safety requirements outlined in Section 7.2 - Assessing and Recording Adverse Events.

### 7.1.5.2 Blinding/Unblinding

This is an open label trial; there is no blinding for this trial.

### 7.1.5.3 Calibration of Critical Equipment

The investigator or qualified designee has the responsibility to ensure that any critical device or instrument used for a clinical evaluation/test during a clinical trial that provides important information about inclusion/exclusion criteria and/or safety or efficacy parameters shall be suitably calibrated and maintained to ensure that the data obtained is reliable and/or reproducible. Documentation of equipment calibration must be retained as source documentation at the trial site.

Critical Equipment for this trial includes:

- Laboratory equipment – as required for inclusion laboratory tests and trial assessments

# Proprietary Information of MD Anderson

Protocol # 2016-0251

Date: February 24, 2020

103

- Imaging equipment – as required for trial objectives

See protocol-specified guidance in the Administrative Binder, Procedures Manual, Pharmacy Manual and SIM.

## 7.1.6 Visit Requirements

Visit requirements are outlined in Section 6.0 - Trial Flow Chart. Specific procedure-related details are provided above in Section 7.1 - Trial Procedures.

### 7.1.6.1 Screening

#### 7.1.6.1.1 Screening Period

#### 7.1.6.2 Screening Visit

Within 28 days prior to treatment allocation, potential subjects will be evaluated to determine that they fulfill the entry requirements as set forth in Section 5.1. Visit requirements are outlined in the Trial Flow Chart (Section 6.0). Screening procedures may be repeated.

Written consent must be obtained prior to performing any protocol-specific procedure. Results of a test performed prior to the subject signing consent as part of routine clinical management are acceptable in lieu of a screening test if performed within the specified time frame. Screening procedures are to be completed within 28 days prior to the first dose of trial treatment except for the following:

- Laboratory tests are to be performed within 10 days prior to the first dose of trial treatment. An exception is hepatitis testing which may be done up to 28 days prior to the first dose of trial treatment.
- Evaluation of ECOG is to be performed within 7 days prior to the first dose of trial treatment.
- For women of reproductive potential, a urine or serum pregnancy test will be performed within 72 hours prior to the first dose of trial treatment. If urine pregnancy results cannot be confirmed as negative, a serum pregnancy test will be required (performed by the local trial site laboratory).
- To meet the requirement for the submission of tumor tissue from a newly obtained core needle biopsy specimen, the tissue sample must have been collected since the completion of the most recent cancer therapy.
- HCV GT determination and resistance GT detection must be performed prior to the first dose of treatment on Day 1.

Subjects may be rescreened after initially failing to meet the inclusion/exclusion criteria. Results from assessments performed during the initial screening period are acceptable in lieu of repeat screening test if performed within the specified time frame and the

# Proprietary Information of MD Anderson

Protocol # 2016-0251

Date: February 24, 2020

104

inclusion/exclusion criteria is met. Subjects who are rescreened will retain their original screening number. Results of a test performed prior to the subject signing consent as part of routine clinical management are acceptable in lieu of a screening test if performed within the specified time frame.

## 7.1.6.3 Treatment Period

Visit requirements are outlined in the Trial Flow Chart (Section 6.0). Specific procedure-related details are provided above in the Trial Procedures (Section 7.1 - Trial Procedures).

Subjects are eligible for up to 35 cycles (approximately 2 years) of treatment on pembrolizumab.

## 7.1.6.4 Post-Treatment Visits

### 7.1.6.4.1 Safety Follow-up Visits

The mandatory Safety Follow-up Visit should be conducted approximately 30 days after the last dose of trial treatment or before the initiation of a new anticancer treatment, whichever comes first.

All AEs that occur prior to the Safety Follow-Up Visit should be recorded. Subjects with an AE of Grade >1 will be followed until the resolution of the AE to Grade 0-1 or until the beginning of a new anticancer therapy, whichever occurs first. Serious AEs that occur within 90 days of the end of treatment or before initiation of a new anticancer treatment should also be followed and recorded.

### 7.1.6.4.2 Follow-up visits

Subjects who discontinue trial treatment for a reason other than disease progression will move into the Follow-Up Phase and should be assessed approximately Q9W by radiologic imaging to monitor disease status. Every effort should be made to collect information regarding disease status until the start of new anti-cancer therapy, disease progression, death, or the end of trial, whichever occurs first. Information regarding post-trial anticancer treatment will be collected if new treatment is initiated.

### 7.1.6.4.3 Survival Follow-up

Subjects who experience confirmed disease progression or start a new anticancer therapy, will move into the Survival Follow-Up Phase and should be contacted by telephone approximately Q12W to assess for survival status until death, withdrawal of consent, or the end of the trial, whichever occurs first.

# Proprietary Information of MD Anderson

Protocol # 2016-0251

Date: February 24, 2020

105

## 7.1.6.5 Survival Status

To ensure current and complete survival data is available at the time of database locks, updated survival status may be requested during the course of the study by Merck. For example, updated survival status may be requested prior to but not limited to an external Data Monitoring Committee (eDMC) review, interim and/or final analysis. Upon Merck notification, all subjects who do not/will not have a scheduled study visit or study contact during the Merck-defined time period will be contacted for their survival status (excluding subjects that have a previously recorded death event in the collection tool).

## 7.2 Assessing and Recording Adverse Events

### 7.2.1 Adverse Events

An AE is defined as any untoward medical occurrence in a patient or clinical investigation subject administered a pharmaceutical product and which does not necessarily have to have a causal relationship with this treatment. An AE can therefore be any unfavorable and unintended sign (including an abnormal laboratory finding, for example), symptom, or disease temporally associated with the use of a medicinal product or protocol-specified procedure, whether or not considered related to the medicinal product or protocol-specified procedure. Any worsening (ie, any clinically significant adverse change in frequency and/or intensity) of a preexisting condition that is temporally associated with the use of Merck's product, is also an AE.

Changes resulting from normal growth and development that do not vary significantly in frequency or severity from expected levels are not to be considered AEs. Examples of this may include, but are not limited to, teething, typical crying in infants and children, and onset of menses or menopause occurring at a physiologically appropriate time.

Merck's product includes any pharmaceutical product, biological product, device, diagnostic agent or protocol-specified procedure, whether investigational (including placebo or active comparator medication) or marketed, manufactured by, licensed by, provided by or distributed by Merck for human use.

Adverse events may occur during clinical trials, or as prescribed in clinical practice, from overdose (whether accidental or intentional), from abuse and from withdrawal.

Progression of the cancer under study is not considered an AE.

All AEs that occur after the ICF is signed but before treatment allocation must be reported by the investigator if they cause the subject to be excluded from the trial, or are the result of a protocol-specified intervention, including but not limited to washout or discontinuation of usual therapy, diet, placebo treatment or a procedure.

From the start of treatment through 30 days following cessation of treatment, all AEs must be reported by the investigator. Such events will be recorded at each examination on the AE CRF.

# Proprietary Information of MD Anderson

Protocol # 2016-0251

Date: February 24, 2020

106

The reporting timeframe for AEs meeting any serious criteria is described in Section 7.2.4.1. The investigator will make every attempt to follow all subjects with non-serious AEs for outcome.

Adverse events will not be collected for subjects during the pre-screening period (for determination of archival tissue status) as long as that subject has not undergone any protocol-specified procedure or intervention. If the subject requires a blood draw, fresh tumor biopsy etc., the subject is first required to provide consent to the main study and AEs will be captured according to guidelines for standard AE reporting.

## 7.2.2 Definition of an Overdose

For this trial, an overdose of pembrolizumab will be defined as any dose of 1000 mg or greater ( $\geq 5$  times the indicated dose).

No specific information is available on the treatment of overdose of pembrolizumab. In the event of overdose, the subject should be observed closely for signs of toxicity. Appropriate supportive treatment should be provided if clinically indicated.

In this trial, an overdose of other agents is any dose higher than intake in excess of the prescribed dose of Zepatier or RBV per calendar day.

## 7.2.3 Reporting of Pregnancy and Lactation to Merck

Although pregnancy and infant exposure during breastfeeding are not considered AEs, any pregnancy or infant exposure during breastfeeding in a subject (spontaneously reported to the investigator or their designee) that occurs during the trial, through 120 days following cessation of treatment, or 30 days following cessation of treatment if the subject initiates new anticancer therapy, whichever is earlier, are reportable to Merck.

All reported pregnancies must be followed to the completion/termination of the pregnancy. Pregnancy outcomes of spontaneous abortion, missed abortion, benign hydatidiform mole, blighted ovum, fetal death, intrauterine death, miscarriage and stillbirth must be reported as serious events (Important Medical Events). If the pregnancy continues to term, the outcome (health of infant) must also be reported.

The study investigator will make every effort to obtain permission to follow the outcome of the pregnancy and report the condition of the fetus or newborn to Merck. If a male subject impregnates his female partner the study personnel at the site must be informed immediately and the pregnancy reported to Merck and followed as described above.

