# Proprietary Information of MD Anderson

Protocol # 2016-0251

Date: February 24, 2020

40

cirrhosis by the above criteria, a liver biopsy is required. Liver biopsy results supersede the results obtained by Fibroscan or Fibrosure.

9. Have a predicted life expectancy of greater than 3 months.
10. Have measurable disease based on RECIST 1.1 as confirmed by the blinded M.D. Anderson radiology. Target lesions situated in a previously irradiated area are considered measurable if progression has been demonstrated in such lesions.

Note: the same image acquisition and processing parameters should be used throughout the study for a given subject..

11. Have a performance status of 0 or 1 using the ECOG Performance Scale within 7 days of first dose of study drug.
12. Have documented objective radiographic progression after stopping treatment with sorafenib or else intolerance to sorafenib. Intolerance to sorafenib is defined as: NCI CTCAE version 4.0 (Section 12.4) Grade  $\geq 2$  drug-related AE(s) which both a) persisted in spite of comprehensive supportive therapy according to institutional standards and b) persisted or recurred after sorafenib treatment interruption of at least 7 days and dose reduction by one dose level. Patients treated on sorafenib as the last treatment may start pembrolizumab at least 14 days after the last dose of sorafenib.
13. For Arm B Subjects with chronic active infection by HCV who are untreated or treated are allowed on study
14. Subjects with a past or resolved hepatitis B virus (HBV) infection, defined as having a negative HBsAg test and a positive total hepatitis B core antibody (HBcAb) test and negative HBV DNA test at screening, are eligible for the study.
15. Female subjects of childbearing potential must have a negative urine or serum pregnancy test within 72 hours prior to receiving the first dose of trial medication. If the urine test is positive or cannot be confirmed as negative, a serum pregnancy test will be required.
16. Male subjects of childbearing potential must agree to use an adequate method of contraception as outlined in Section 5.6.3 - Contraception, starting with the first dose of trial therapy through 120 days (Arm A) or 180 days (Arm b) after the last dose of trial therapy.

Note: Abstinence is acceptable if this is the usual lifestyle and preferred contraception for the subject.

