# Proprietary Information of MD Anderson

Protocol # 2016-0251

Date: February 24, 2020

44

21. Is pregnant or breastfeeding, or expecting to conceive or father children within the projected duration of the trial, starting with the screening visit through 120 days after the last dose of trial treatment.
22. Has received prior therapy with an anti-PD-1, anti-PD-L1, or anti-PD-L2 agent or with an agent directed to another stimulatory or co-inhibitory T cell receptor (eg, CTLA-4, OX-40, CD137)..
23. Has severe hypersensitivity ( $\geq$ Grade 3) to pembrolizumab and/or any of its excipients.
24. Has a known history of human immunodeficiency virus (HIV) infection. No HIV testing is required unless mandated by local health authority.
25. Has a known history of active tuberculosis (TB; *Bacillus tuberculosis*).
26. Has received a live vaccine within 30 days prior to the first dose of trial drug. Examples of live vaccines include, but are not limited to, the following: measles, mumps, rubella, varicella/zoster (chicken pox), yellow fever, rabies, *Bacillus Calmette–Guérin* (BCG), and typhoid vaccine. Seasonal influenza vaccines for injection are generally killed virus vaccines and are allowed; however, intranasal influenza vaccines (eg, FluMist®) are live attenuated vaccines and are not allowed.
27. Has untreated active HBV.

Note: Antiviral therapy for HBV must be given for at least 3 months prior to first dose of study drug, and HBV viral load must be less than 100 IU/mL prior to first dose of study drug. Those on active HBV therapy with viral loads under 100 IU/mL should stay on the same therapy throughout study treatment. HBsAg, HBsAb, anti-HBe, anti-HBc and HBV DNA must be measured at baseline and during the study. Those subjects who are anti-HBc (+) and negative for HBsAg and HBV DNA do not require HBV prophylaxis, but need monitoring with HBsAg, HBsAb, anti-HBe, anti-HBc, and HBV DNA

28. HCV-positive subjects received a prior NS5A-containing regimen.
29. Has received a live vaccine within 30 days of planned start of study therapy (Cycle 1, Day 1). Note: The killed virus vaccines used for seasonal influenza vaccines for injection are allowed; however intranasal influenza vaccines (e.g., FluMist®) are live attenuated vaccines and are not allowed.
30. Subjects with a history of significant or unstable cardiac disease are excluded due to the hemolytic anemia associated with RBV. Subjects with proven coronary artery disease or angina.

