### 5.6.3 Contraception

Pembrolizumab may have adverse effects on a fetus in utero.

For this trial, male subjects will be considered to be of non-reproductive potential if they have azoospermia (whether due to having had a vasectomy or due to an underlying medical condition).

Female subjects will be considered of non-reproductive potential if they meet 1 of the following criteria:

- She is postmenopausal, defined as at least 12 months with no menses without an alternative medical cause. In women <45 years of age who are not using hormonal contraception or hormonal replacement therapy, a high follicle stimulating hormone (FSH) level in the postmenopausal range may be used to confirm a post-menopausal state. In the absence of 12 months of amenorrhea, a single FSH measurement is insufficient.
- She had a hysterectomy and/or bilateral oophorectomy, bilateral salpingectomy or bilateral tubal ligation/occlusion, at least 6 weeks prior to screening.
- She has a congenital or an acquired condition that prevents childbearing.

Female and male subjects of reproductive potential must agree to avoid becoming pregnant or impregnating a partner, respectively, while receiving trial drug and for 120 days after the last dose of trial drug by complying with 1 of the following:

- Practice abstinence from heterosexual activity.

Abstinence (relative to heterosexual activity) can be used as the sole method of contraception if it is consistently employed as the subject's preferred and usual lifestyle and if considered acceptable by local regulatory agencies and IRBs/ERCs. Periodic abstinence (eg, calendar, ovulation, symptothermal, post-ovulation methods, etc.) and withdrawal are not acceptable methods of contraception.

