# Proprietary Information of MD Anderson

Protocol # 2016-0251

Date: February 24, 2020

72

- Use (or have their partner use) acceptable contraception during heterosexual activity.

Acceptable methods of contraception are‡:

- Single method (1 of the following is acceptable):
  - IUD
  - Vasectomy of a female subject's male partner
  - Contraceptive rod implanted into the skin
- Combination method (requires use of 2 of the following):
  - Diaphragm with spermicide (cannot be used in conjunction with cervical cap/spermicide)
  - Cervical cap with spermicide (nulliparous women only)
  - Contraceptive sponge (nulliparous women only)
  - Male condom or female condom (cannot be used together)
  - Hormonal contraceptive: oral contraceptive pill (estrogen/progestin pill or progestin-only pill), contraceptive skin patch, vaginal contraceptive ring, or subcutaneous contraceptive injection

‡If a contraceptive method listed above is restricted by local regulations/guidelines, then it does not qualify as an acceptable method of contraception for subjects participating at sites in this country/region.

Subjects should be informed that taking the trial medication may involve unknown risks to the fetus (unborn baby) if pregnancy were to occur during the trial. In order to participate in the trial, subjects of childbearing potential must adhere to the contraception requirement (described above) from the day of trial medication initiation (or 14 days prior to the initiation of trial medication for oral contraception) throughout the trial period up to 120 days (Arm A) or 180 days (Arm B) after the last dose of trial medication. If there is any question that a subject of childbearing potential will not reliably comply with the requirements for contraception, that subject should not be entered into the trial.

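### Arm B contraception runs to 180 days in some sections and 120 in others, and reporting of a subject's own pregnancy stops at 120 days, or 30 if new anticancer therapy starts

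*Combined protocol and SAP*

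**What the plan says.** The contraception period is stated in several places.

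- **Inclusion 16** (male subjects): "through 120 days (Arm A) or 180 days (Arm b) after the last dose of trial therapy". **Inclusion 17** gives the same split for both sexes. **Inclusion 18** requires double barrier contraception for 6 months after the last dose in Arm B subjects on ribavirin (RBV).
- **Section 5.6.3, opening rule**, for all subjects of reproductive potential: "while receiving trial drug and for 120 days after the last dose of trial drug". There is no arm split.
- **Section 5.6.3, closing paragraph**: "up to 120 days (Arm A) or 180 days (Arm B) after the last dose of trial medication". This is a condition of entry: "In order to participate in the trial, subjects of childbearing potential must adhere to the contraception requirement".
- **Exclusion 21** bars subjects who expect to conceive or father a child in a window "starting with the screening visit through 120 days after the last dose of trial treatment", again with no arm split.

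Section 7.2.3 sets the reporting period. A pregnancy is reportable if it is "in a subject (spontaneously reported to the investigator or their designee) that occurs during the trial, through 120 days following cessation of treatment". A second limit follows: "or 30 days following cessation of treatment if the subject initiates new anticancer therapy, whichever is earlier, are reportable to Merck". Partner pregnancies have their own sentence, with no end date: "If a male subject impregnates his female partner the study personnel at the site must be informed immediately and the pregnancy reported to Merck".

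**The concern.** There are two problems. First, 5.6.3 is the section staff would use to counsel subjects during the study, and it gives Arm B both 120 and 180 days. A reader who stops at the opening rule tells an Arm B subject she may stop contraception 60 days before the protocol allows.

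Second, the protocol asks Arm B subjects to avoid pregnancy for 180 days but does not require the site to tell Merck about a subject's own pregnancy after day 120. Section 7.2.3 requires follow-up to outcome for reported pregnancies, so that duty lapses with the reporting duty. The outcome of a pregnancy conceived inside the protocol's own precaution window could go unrecorded. The new-therapy clause shortens reporting further, in both arms.

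Scheduled testing would not reliably fill the gap. The last test fixed for all subjects (7.1.3.1.1) is 30 days post treatment. The monthly monitoring recommended for RBV-treated women (7.1.3.1) has no stated end. Late pregnancies would come to light mainly through spontaneous report.

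**Working it through.** The plan gives no figure of its own to reproduce. The check compares the stated windows.

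**Inputs (days after last dose or end of treatment)**

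| Source | Arm A | Arm B |
|---|---|---|
| Inclusions 16 and 17; 5.6.3 closing paragraph | 120 | 180 |
| 5.6.3 opening rule; exclusion 21 | 120 | 120 |
| 7.2.3 reporting, no new therapy | 120 | 120 |
| 7.2.3 reporting, new anticancer therapy | 30 | 30 |

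**Contradiction in 5.6.3 for Arm B:** 180 − 120 = 60 days between the two end dates.

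**Reporting gap = contraception window − reporting limit**

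| Case | Now | After the fix |
|---|---|---|
| Arm B, no new therapy | 180 − 120 = 60 (60/180 = 33%) | 180 − 180 = 0 |
| Arm B, new therapy by day 30 | 180 − 30 = 150 (150/180 = 83%) | 150 |
| Arm A, no new therapy | 120 − 120 = 0 | 0 |
| Arm A, new therapy by day 30 | 120 − 30 = 90 (90/120 = 75%) | 90 |

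**New therapy starting later.** Section 7.2.3 does not say whether a start after day 30 ends reporting retrospectively. If it acts only from the start day s, the current Arm B gap is 180 − min(120, max(30, s)): 150 days at s = 30, 120 at s = 60, 90 at s = 90, and 60 from s = 120 onward.

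**If the extra 60 days was meant only for the antivirals.** This is an assumption; inclusion 17 refers to study medication generally. On this reading the 180 days count from the last antiviral dose, while 7.2.3 counts 120 days from the end of all treatment. There is no gap if the last pembrolizumab dose falls at least 180 − 120 = 60 days after the last antiviral dose. With cycle k on day 1 + 21(k − 1):

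- 12-week course, ending day 84: pembrolizumab is needed on or after day 84 + 60 = 144. Cycle 7 is day 127 (gap 144 − 127 = 17 days); cycle 8 is day 148 (gap 0).
- 16-week course, ending day 112: pembrolizumab is needed on or after day 112 + 60 = 172. Cycle 9 is day 169 (gap 172 − 169 = 3 days); cycle 10 is day 190 (gap 0).

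The no-new-therapy gap would then affect only Arm B subjects whose last pembrolizumab dose comes before cycle 8 or cycle 10. Such stopping is plausible. The first scan is at 9 weeks with progression confirmed 4 to 8 weeks later (7.1.4.1.2), that is 63 + 28 = day 91 to 63 + 56 = day 119. In the pembrolizumab study cited in 4.3.1, 34 of 104 patients had progressive disease.

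**Could another rule cover days 121 to 180?**

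- Section 5.6.4 deals with a subject who becomes pregnant during pembrolizumab treatment, not afterwards.
- Under 7.2.3 pregnancy is not itself an adverse event. After day 90, section 7.2.4.1 requires only treatment-related serious events to go to the IND Office. An uncomplicated pregnancy is not captured.
- Reading the reference in 7.2.3 to events during the trial as covering all follow-up would leave the 120-day limit in the same sentence with no effect.

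**The case against.** The strongest reply is that the 5.6.3 texts can be reconciled. The opening rule follows a sentence on pembrolizumab's fetal risk, and the closing paragraph can be read as a specific rule refining a general one. A subject who complies for 180 days also satisfies 120. Inclusion 18 adds support for the longer period in RBV-treated subjects, and exclusion 21 tests intent at entry rather than setting an end date on study. Much of this stands: eligibility stays decidable because the criteria are cumulative, and the intended Arm B period is clearly 180 days. But the opening rule is addressed to all subjects and to trial drug generally, with no exception for Arm B, so the wrong instruction remains in print.

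On reporting, nothing in the documents says the reporting window must equal the contraception window. The 30-day clause mirrors the rule for collecting serious adverse events and looks deliberate. That is a fair reason to leave the clause to the sponsor. It does not explain the 120-day limit, which matches Arm A exactly and takes no account of Arm B's longer period.

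The practical effect is also small. Subjects remain in contact through follow-up visits or calls, which allow a spontaneous report although no pregnancy question is required. Related serious events still reach the IND Office, and partner pregnancies have no stated cut-off. This limits how often the gap would matter but does not close it.

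**Conclusion.** The point holds. Section 5.6.3 contradicts itself for Arm B by 60 days, and exclusion 21 carries the shorter figure. Section 7.2.3 leaves 60 of 180 days (33%) of Arm B's required contraception period without a duty to report a subject's own pregnancy. With new anticancer therapy started by day 30, the gap is 150 of 180 days in Arm B and 90 of 120 in Arm A; those figures come wholly from the 30-day clause.

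The 60-day figure takes the arm-specific text at face value, counting 180 days from the last dose of any trial drug. On the antiviral-only assumption it narrows to Arm B subjects who stop pembrolizumab early. It concerns women of childbearing potential among about 15 Arm B subjects; the documents give no count. This is a participant-safety and consistency correction that should be made. No estimate, interval or stopping rule is affected.

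**What to change.** State 120 days for Arm A and 180 days for Arm B, counted from the last dose of any trial drug, in three places: exclusion 21, the opening rule of 5.6.3, and the reporting period in 7.2.3.

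The cost is a wording amendment and 60 more days of passive pregnancy reporting in Arm B, with no added visits or tests.

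This leaves the 30-day new-therapy cut-off in place, so up to 150 days in Arm B and 90 in Arm A stay outside reporting for subjects who start new treatment. The sponsor should decide separately, for both arms, whether to keep that cut-off.
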